6.1.1. Pseudo Code

The following SAS® pseudo code will be used to calculate the following for safety analyses:

Chi-Square test at 5% two-sided significance level:

```
proc freq;
    Table treatment*analysis_variable / chisq;
    ods output ChiSq=outputdsn;
run;
```

Fisher's Exact test at 5% two-sided significance level:

```
proc freq;
    Table treatment*analysis_variable / exact;
    ods output FishersExact=outputdsn;
run;
```

95% Wilson CI for proportions/percents:

```
Proc freq;
    Table treatment*analysisvariable / binomial(wilson);
    ods output binomialcls=outputdsn;
Run;
```

95% Wilson CI for difference in proportions (produces Newcombe CI):

```
Proc freq;
    Table treatment*analysisvariable / riskdiff(cl=Wilson);
    Exact Riskdiff;
    ods output pdiffcls=outputdsn;
Run;
```

95% Exact Blaker CI for proportions/percents:

```
Proc freq;
  Table treatment*analysisvariable / binomial(blaker);
  ods output binomialcls=outputdsn;
Run;
```

Odds ratios using ordinal logistic regression:

```
PROC LOGISTIC data=dataset;
  Class treatment (ref='Placebo') baseline(ref='None') / param=reference;
  Model severity_postvaca1=baseline treatment;
Run;
```

```
PROC LOGISTIC data=dataset;
  Class treatment (ref='Placebo') baseline(ref='None') / param=reference;
  Model severity_postvac2=baseline treatment;
Run;
```

See Section 8 for pseudocode to be used in the efficacy analyses.

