The proportion of subjects with laboratory results meeting toxicity grading criteria will be presented for each biochemistry and hematology parameter by HCV Infection status, visit, toxicity grade, and treatment group in [Table 86](#), [Table 87](#), [Table 90](#), and [Table 91](#), respectively. The proportion of subjects with laboratory results related to study product meeting toxicity grading criteria will be presented for each biochemistry parameter in [Table 88](#) and [Table 89](#) and each hematology parameter in [Table 92](#) and [Table 93](#) by HCV Infection status, severity, study day and treatment group. Descriptive statistics including mean, standard deviation, median, mean change from baseline and associated standard deviation by timepoint, for each laboratory parameter, will be summarized by HCV Infection status and treatment group in [Table 94](#), [Table 95](#), [Table 96](#), [Table 97](#), [Table 98](#), [Table 99](#), [Table 100](#), [Table 101](#), by treatment group. Laboratory values will be presented by visit and treatment group in [Figure 31](#), [Figure 32](#), [Figure 33](#), [Figure 34](#), [Figure 35](#), [Figure 36](#), [Figure 37](#), [Figure 38](#), [Figure 39](#), and [Figure 40](#). Shift tables by time point, based on the normal ranges provided by the clinical laboratory, are presented in [Table 102](#), [Table 103](#), [Table 104](#), and [Table 105](#).

The denominator for proportions is the number of subjects with each specific laboratory parameter at the visit. Additionally, graded results will be analyzed as a multinomial variable (Grade 0, Grade 1, Grade 2, Grade 3 and above) using ordinal logistic regression to make treatment group comparisons. The odds of a lab parameter being in a higher level severity among subjects receiving vaccine compared to placebo will be calculated ([Table 106](#), [Table 107](#), [Table 108](#), [Table 109](#)). The covariates that will be used are treatment group

and baseline laboratory severity. The proportional odds assumption will be tested to show whether or not the relationship between each pair of outcome groups is the same.

The model described above will be fit for each laboratory parameter and estimates of which factors influence severity at baseline and one month after each vaccination will be obtained using PROC LOGISTIC following the pseudocode in Section 6.1.1.

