- In the “If Not Related, Alternate Etiology” column, merge the 2 data fields for collecting alternate etiology, separate by a colon.
- Listing will include deaths, as they are SAEs, but we will also include a separate death listing below to highlight them

Tables with similar format:

Table 84: Listing of Deaths

Section 14.3.5 Displays of Laboratory Results

Table 85: Proportion of Subjects Reporting Laboratory Adverse Events Following the First Dose of Study Product by Treatment Group - Safety Population

Dose Number	Treatment Group	Number of Subjects with Laboratory AEs n	Number of Subjects N	Proportion of Subjects with Laboratory AEs	Proportion of Subjects with Laboratory AEs 95% CI	Difference in Proportion of Subjects with Laboratory AEs between Vaccine and Placebo	Difference in Proportion of Subjects with Laboratory AEs between Vaccine and Placebo 95% CI
Baseline	Vaccine	x	x	0.xx	0.xx, 0.xx	0.xx	0.xx, 0.xx
	Placebo	x	x	0.xx	0.xx, 0.xx	--	--
	All Subjects	x	x	0.xx	0.xx, 0.xx	--	--
Post Either Dose	Vaccine	x	x	0.xx	0.xx, 0.xx	0.xx	0.xx, 0.xx
	Placebo	x	x	0.xx	0.xx, 0.xx	--	--
	All Subjects	x	x	0.xx	0.xx, 0.xx	--	--
Post Dose 1	Vaccine	x	x	0.xx	0.xx, 0.xx	0.xx	0.xx, 0.xx
	Placebo	x	x	0.xx	0.xx, 0.xx	--	--
	All Subjects	x	x	0.xx	0.xx, 0.xx	--	--
Post Dose 2	Vaccine	x	x	0.xx	0.xx, 0.xx	0.xx	0.xx, 0.xx
	Placebo	x	x	0.xx	0.xx, 0.xx	--	--
	All Subjects	x	x	0.xx	0.xx, 0.xx	--	--

Notes: The denominator for proportions is based on the number of subjects enrolled in the safety population in the respective treatment group and dose number with non-missing laboratory data for the specified timepoint.

Table 86: Biochemistry Laboratory Results by Parameter, Maximum Severity, Visit, and Treatment Group – Safety Population-Uninfected HCV Status*

Visit	Laboratory Parameter	Toxicity Grade	Vaccine (N=X)		Placebo (N=X)		All Subjects (N=X)	
			n	%	n	%	n	%
Visit 1	Alanine Transferase (SGPT) (U/L)	Total Subjects with Data	x	100	x	x	x	x
		None	x	x	x	x	x	x
		Toxicity Grade 1	x	x	x	x	x	x
		Toxicity Grade 2	x	x	x	x	x	x
		Toxicity Grade 3	x	x	x	x	x	x
		Toxicity Grade 4	x	x	x	x	x	x
	Creatinine (mg/dL)	Total Subjects with Data	x	100	x	x	x	x
		None	x	x	x	x	x	x
		Toxicity Grade 1	x	x	x	x	x	x
		Toxicity Grade 2	x	x	x	x	x	x
		Toxicity Grade 3	x	x	x	x	x	x
		Toxicity Grade 4	x	x	x	x	x	x
Continue through Visit 26...								

Notes: * Uninfected HCV Status: all laboratory results collected prior to confirmed HCV infection are summarized

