Visit 4	Normal to Low	Hemoglobin (g/dL)	x/x (x)	x/x (x)	x/x (x)
		Platelet Counts (10 ³ cells/mm ³)	x/x (x)	x/x (x)	x/x (x)
		White Blood Cells (10 ³ cells/μL)	x/x (x)	x/x (x)	x/x (x)
	Normal to High	Hemoglobin (g/dL)	x/x (x)	x/x (x)	x/x (x)
		Platelet Counts (10 ³ cells/mm ³)	x/x (x)	x/x (x)	x/x (x)
		White Blood Cells (10 ³ cells/μL)	x/x (x)	x/x (x)	x/x (x)
Continue for all study Visits					

Notes: * Uninfected HCV Status: all laboratory results collected prior to confirmed HCV infection are summarized
 NN = Number of subjects with normal laboratory test results at Baseline and laboratory test results available at the Visit being summarized.
 n = Number of subjects with the observed case.
 Percentages are based on NN

Table 105: Summary of Hematology Laboratory Test Shifts of Laboratory Values from Baseline by Site - Infected HCV Status* - Safety Population

Visit	Shift Category	Laboratory Test	Vaccine (N=X) n/NN (%)	Placebo (N=X) n/NN (%)	All Subjects (N=X) n/NN (%)
H02	Normal to Low	Hemoglobin (g/dL)	x/x (x)	x/x (x)	x/x (x)
		Platelet Counts (10 ³ cells/mm ³)	x/x (x)	x/x (x)	x/x (x)
		White Blood Cells (10 ³ cells/μL)	x/x (x)	x/x (x)	x/x (x)
	Normal to High	Hemoglobin (g/dL)	x/x (x)	x/x (x)	x/x (x)
		Platelet Counts (10 ³ cells/mm ³)	x/x (x)	x/x (x)	x/x (x)
		White Blood Cells (10 ³ cells/μL)	x/x (x)	x/x (x)	x/x (x)
Continue for all study Visits					

Notes: * Infected HCV Status: all laboratory results collected after confirmed HCV infection and during the HCV cohort are summarized
 NN = Number of subjects with normal laboratory test results at Baseline and laboratory test results available at the Visit being summarized.
 n = Number of subjects with the observed case.
 Percentages are based on NN.

Table 106: Maximum Likelihood Odds Ratio Estimates by Biochemistry Laboratory Parameter-Safety Population- 1 month Post-Vaccination 1

Laboratory Parameter	Maximum Likelihood Estimates		Odds Ratio Estimates	
	Estimate (SE)	P-value	Odds Ratio	95% CI
Alanine Transferase (SGPT) (U/L)	x.x (x.x)	0.xxx	x.x	x.x, x.x
Creatinine (mg/dL)	x.x (x.x)	0.xxx	x.x	x.x, x.x
Continue for all parameters...				

Tables with similar format:

Table 107: Maximum Likelihood and Odds Ratio Estimates by Biochemistry Laboratory Parameter-Safety Population- 1 month Post-Vaccination 2

Table 108: Odds Ratio Estimates by Hematology Laboratory Parameter-Safety Population- 1 month Post-Vaccination 1

Laboratory Test	Maximum Likelihood Estimates		Odds Ratio Estimates	

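### The laboratory ordinal-logistic code sets no response order, so with the SAP's own grade labels Tables 106–109 would print the reciprocal of the odds ratio that SAP 9.6 describes

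*SAP*

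**What the plan says.** SAP 9.6 (Clinical Laboratory Evaluations) plans that "graded results will be analyzed as a multinomial variable (Grade 0, Grade 1, Grade 2, Grade 3 and above) using ordinal logistic regression", with treatment group and baseline severity as covariates. It states the target: "The odds of a lab parameter being in a higher level severity among subjects receiving vaccine compared to placebo will be calculated". The estimates are to be "obtained using PROC LOGISTIC following the pseudocode in Section 6.1.1" and reported in Tables 106–109.

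SAP 6.1.1 (Pseudo Code) contains two PROC LOGISTIC calls. Both use "Class treatment (ref='Placebo') baseline(ref='None') / param=reference". The model lines are "Model severity_postvaca1=baseline treatment" and "Model severity_postvac2=baseline treatment". Neither response carries a DESCENDING, ORDER= or EVENT= option, and the SAP does not say how the severity variables are stored. SAP 13 specifies SAS 9.4 or later, so SAS defaults apply wherever the code is silent.

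The shell titled "Maximum Likelihood Odds Ratio Estimates by Biochemistry Laboratory Parameter-Safety Population- 1 month Post-Vaccination 1" (Table 106) and the three that follow it head the result column simply as an odds ratio, with no direction.

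**The concern.** The prose and the code it points to do not secure the same quantity. The treatment contrast is right, because placebo is the reference level. The direction of the response, however, is left to the software default. If that default runs opposite to the prose, a reader who takes the column as SAP 9.6 describes it would see a worsening of laboratory grades on vaccine as an odds ratio below 1, and an improvement as one above 1.

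This matters because laboratory adverse events one month after each vaccination are a primary safety endpoint (SAP 3.2), and Protocol 11.1 says the null hypothesis will be tested for the primary safety endpoints. The Table 85 shell gives a between-group difference with a confidence interval but no p-value. The treatment p-values planned for laboratory results are therefore those in Tables 106–109, beside the odds ratios whose direction is in doubt. Five parameters at two time points give 5 × 2 = 10 odds ratios.

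**Working it through.** **No stated figure to reproduce.** The documents give no expected grade distribution or odds ratio for laboratory results, so the distributions below are assumptions. The reversal itself does not depend on them.

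**Inputs**

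- Response levels: Grade 0, 1, 2, 3 and above (SAP 9.6), or None followed by "Toxicity Grade 1" up to Grade 4 (Table 86 shell). Both sets sort ascending, numerically or as text, since N precedes T.
- Treatment reference: placebo (SAP 6.1.1).
- Software default, not stated in the documents: for a response with more than two levels, PROC LOGISTIC models cumulative probability over the lower ordered values.

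**Step 1: what the code fits.** With ascending grades the default model is

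logit P(Y ≤ j) = a_j + b·vaccine + baseline terms,

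so exp(b) is the odds ratio for a *lower* grade on vaccine. Since logit P(Y ≤ j) = −logit P(Y > j), the odds ratio for a *higher* grade is exp(−b) = 1/exp(b). Confidence limits invert in the same way, and the p-value for b = 0 is unchanged. The baseline covariate does not alter this identity.

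**Step 2: one case by hand.** Assume placebo grades 0/1/2/3+ of 85/10/4/1% and a true odds ratio of 2 for higher grade.

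| Cut | Placebo odds of higher | Vaccine odds of higher (× 2) | Placebo odds of lower | Vaccine odds of lower | Ratio of lower odds |
|---|---|---|---|---|---|
| 0 vs ≥1 | 15/85 = 0.1765 | 0.3529 | 5.667 | 2.833 | 0.50 |
| ≤1 vs ≥2 | 5/95 = 0.0526 | 0.1053 | 19.0 | 9.5 | 0.50 |
| ≤2 vs ≥3 | 1/99 = 0.0101 | 0.0202 | 99.0 | 49.5 | 0.50 |

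The code as written prints 0.50 where SAP 9.6 describes 2.00.

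**Step 3: fitted by maximum likelihood.** Expected counts with 270 per arm, under three assumed placebo distributions (85/10/4/1, 95/3/1.5/0.5 and 70/20/7/3%). The model was fitted without a baseline covariate. Ranges are across the three distributions.

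| Response coding, default order | True 1.5 | True 2 | True 3 |
|---|---|---|---|
| Grade 0–3, or None/Toxicity Grade 1–3 (ascending) | 0.667 | 0.500 | 0.333 |
| Same, with descending order | 1.50 | 2.00 | 3.00 |
| None/Mild/Moderate/Severe as text (sorts Mild, Moderate, None, Severe) | 1.30–1.40 | 1.52–1.75 | 1.77–2.33 |
| None/Grade 1/Grade 2/Grade 3 as text (None sorts last) | 1.45–1.50 | 1.86–2.00 | 2.56–2.99 |

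The first row is an exact reciprocal under all three distributions. The last two rows keep the direction but on a wrongly ordered scale, with attenuation that ranges from slight to substantial.

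**Step 4: an example with confidence limits.** Assume 250 per arm, grades 80/12/6/2% on vaccine and 88/8/3/1% on placebo. The log odds ratio for higher grade is 0.615, so the odds ratio is exp(0.615) = 1.85 (95% CI 1.13 to 3.02). The default fit with ascending grades prints 1/1.85 = 0.54 (0.33 to 0.88).

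**The case against.** Four points can be made for the plan as it stands.

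*The code is labelled pseudo code, and the prose is unambiguous.* It has placeholders and an apparent typing slip in the dose 1 variable name, so a programmer working to SAP 9.6 could add the option unprompted. That may happen, but SAP 6.1.1 presents the code as what will be used, SAP 9.6 points to it, and the shells state no direction against which an error would show. This lowers the likelihood of harm without removing the contradiction.

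*The reversal depends on a coding the SAP never defines.* This stands. A reader might infer that the code yields the odds of lower severity whatever the data look like. The documents do not support that: some text codings give a same-direction result on a wrong scale. The laboratory labels the SAP prints do sort ascending, however, so the reversal follows from its own terms.

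*The consequence is limited.* This also stands. A reader might infer that the laboratory primary safety result would be turned upside down. Its main between-group comparison is Table 85, with proportions and differences that do not use this model, and the same holds for the grade tables (86–93) and shift tables (102–105). SAP 9.6 introduces the ordinal model as an addition, and Protocol 11.4.2 offers it as one of two options. A reversed odds ratio would conflict visibly with those tables.

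*The example counts are invented.* True. They show scale only and say nothing about what this vaccine does. That toxicity would appear as protection holds only if the vaccine worsens grades and the code is run unchanged on ascending values.

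**Conclusion.** The code in SAP 6.1.1 does not deliver the quantity promised in SAP 9.6. With the SAP's own laboratory labels and the SAS default, each of the ten odds ratios in Tables 106–109 and its limits would be the reciprocal of the one described, and its p-value would be unchanged. With other text labels the scale would be mis-ordered rather than reversed. In every case the response order is left unspecified and needs to be stated.

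The conclusion rests on two things outside the text: the PROC LOGISTIC default, and the response being stored under labels that sort as the SAP prints them. It does not extend to Table 85 or to the grade and shift tables. It should be fixed before the tables are run.

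**What to change.** 1. Code post-vaccination severity numerically 0 to 3, with 3 meaning Grade 3 and above.
2. Add the order to the response in both calls, for example `model severity_postvac1(descending order=internal) = baseline treatment;` and the same for `severity_postvac2`. This also corrects the dose 1 variable name.
3. Make the baseline reference match that coding: use `ref='0'`, or attach a format that maps 0 to None so that the existing reference label still works.
4. Footnote Tables 106–109: an odds ratio above 1 means higher severity on vaccine.

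The cost is a few lines of code and one footnote. Data, design and timing do not change.

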6.2. Timing of Analyses

The final analysis will be performed after database lock when all HCV RNA negative subjects have been followed through Visit 26, the final study visit, at Day 600 (Window: Days 593-607) and when all subjects who are confirmed HCV RNA positive have been followed through visit H09, approximately Day 270 (Window: Days 249-291) after their first HCV-positive quantitative RNA result, and all research laboratory data are received at the SDCC.

6.3. Analysis Populations

A tabular listing of all subjects, visits, and observations excluded from the efficacy analysis will be provided in the CSR along with the reason for exclusion and censoring day, if applicable ([Listing 1](#)). Four analysis populations will be used in the analyses, the Safety, mITT, According to Protocol (ATP), and Immunogenicity. A listing of subjects whose assigned treatment group does not match their randomized treatment group will be provided in [Listing 2](#).

6.3.1. Safety Population

The safety population includes all randomized subjects who received at least one vaccination. In the unlikely event of an error in randomization or study product administration (i.e., incorrect product at either dose), subjects will be grouped by vaccine group if they received one or more doses of vaccine and in the placebo group otherwise.

6.3.2. Modified Intention-to-Treat (mITT) Population

The mITT population will consist of all randomized subjects who receive at least one vaccination, are not HCV infected at the first vaccination, and have sufficient follow-up to be evaluable for efficacy. See Section 3.3.7 for the definition of sufficient follow up. In the unlikely event of an error in randomization or study product administration (i.e., incorrect product), subjects will be grouped by their intended randomized assignment.

6.3.3. According to Protocol Population

The according to protocol (ATP) population is a subset of the mITT analysis cohort, excluding subjects with major protocol deviations that would compromise the assessment of vaccine efficacy (see list below). Subjects who meet any of the criteria listed below will be censored in time to event analyses according to the date of first occurrence of the criteria, and will be excluded from all other types of analyses. The ATP cohort will exclude subjects who:

- a. receive treatment for acute HCV infection;
- b. were enrolled but subsequently found to have been ineligible at enrollment based on a criterion that could reasonably be expected to affect vaccine efficacy (as reviewed by the blinded clinical review team [see below]);
- c. did not receive both doses of vaccine or control;
- d. acquired HCV infection prior to receipt of the second vaccination;
- e. received the wrong (non-randomized) product at either dose;
- f. received the second dose fewer than 42 days or more than 70 days after the first dose;
- g. received an immunosuppressant other than inhaled or topical steroids;
- h. were immunized against another pathogen or received immunoglobulins or other blood products within 14 days of either dose of study vaccine;
- i. have autoimmune disease; and
- j. have a confirmed or suspected immunosuppressive or immunodeficient state.

Membership in the ATP efficacy cohort will be assessed by a centralized, blinded, clinical review team comprised of the site PIs and the sponsor prior to unblinding of the study data.

6.3.4. Immunogenicity Population

The immunogenicity analysis population will consist of all subjects who received any study product and for whom immunogenicity endpoint data are available. If a subject does not receive the second dose, the subject will not be included in the Post-Dose 2 analyses. In the unlikely event of an error in randomization or study product administration (i.e., incorrect product), subjects will be grouped by the product they actually received. In the unlikely event that a subject receives one dose of vaccine and one dose of placebo, the subject will be excluded from immunogenicity analyses.

